### **8.4 Pharmacokinetics**

PK samples will be collected as described in the SoA ([Table 1](#) and [Table 2](#)) and evaluated for magrolimab and oral decitabine/cedazuridine concentrations. Serum magrolimab and plasma decitabine and cedazuridine assessments will be done using validated assays. This could include using leftover serum for alternative PK assay development and analysis.

[Table 13](#) shows the schedule for PK sample collection for serum magrolimab and [Table 14](#) shows assessments for oral decitabine/cedazuridine (for determination of plasma levels of decitabine and cedazuridine). PK collections for oral decitabine/cedazuridine require special pretreatment with tetrahydrouridine (THU, for stabilization) of blood collection tubes and details for this procedure will be included in the Laboratory Manual.

**Table 13: Serum Collection Schedule for Pharmacokinetic Analysis and Antidrug Antibodies (ADA) for Serum Magrolimab**

Day	Dosing Day?	Predose	End of Infusion a
Day 1	Yes	✓	
Day 50	Yes	✓	
Day 57	Yes	✓	✓ (PK Only)
Day 141	Yes	✓	
End of treatment	NA	✓	

NA=not applicable; PK=pharmacokinetic(s).

Note: ✓=PK blood sample is to be collected at the indicated time point.

a Magrolimab should be infused over 3 hours (±30 minutes).

**Table 14: Plasma Collection Schedule for Pharmacokinetic Analysis for Oral Decitabine/Cedazuridine**

Day	Dosing Day?	Predose b	Hours Postdose
Cycle 1 Day 1	Yes	NA	2.0 (±30 minutes) c,d
Cycle 1 Day 4 a,e	Yes	✓ c	0.5 (±5 minutes), 1.0 (±5 minutes) c,d , 1.5 (±5 minutes), 2.0 (±30 minutes) c,d , 3.0 (±10 minutes), 4.0 (±10 minutes) c,d , 6.0 (±20 minutes), 8.0 (±30 minutes)
Cycle 1 Day 5 e	Yes	Predose (24 ±1.0 hours after Cycle 1 Day 4 dose) c	
Cycle 2 Day 4 e	Yes	✓ c	1.0 (±30 minutes) b,c , 2.0 (±30 minutes) c,d , 4.0 (±60 minutes) c,d
Ad-hoc PK sample	NA	NA	Optional (if needed)

ECG=electrocardiogram; NA=not applicable; PK=pharmacokinetic(s).

Notes: ✓=PK blood sample is to be collected at the indicated time point.

a If there are 2 or more dose reductions, then PK should be done on Day 3 and Day 4 instead of Day 4 and Day 5.

b On dosing days, predose samples are to be collected within 60 minutes before administration of study treatment.

c The PK sample is a time-matched blood sample to be taken immediately following (within 5 minutes) the ECG assessment as described in Section 8.2.3.

d ECG assessment is to be taken postdose at this time point.

e If the oral decitabine/cedazuridine dosing level falls below Level 4 (please refer to Table 9 for further details), the timing of PK acquisition at this time point will be adjusted to be 1 day earlier.

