**Table 9: Dosing Reduction Guidelines for Oral Decitabine/Cedazuridine**

Number of Dose Reductions per Individual Subject	Dose per Cycle
Level 1	Oral decitabine/cedazuridine Daily×5 for each 28-day cycle
Level 2	Oral decitabine/cedazuridine Daily×4 for each 28-day cycle
Level 3	Oral decitabine/cedazuridine Daily×3 for each 28-day cycle
Level 4	Oral decitabine/cedazuridine on Days 1, 3, and 5 of each 28-day cycle
Level 5	Discontinue oral decitabine/cedazuridine

DLT=dose-limiting toxicity

Note: For subjects receiving oral decitabine/cedazuridine outside of the period of DLT assessment in the DLT cohort, a maximum of 2 dose reductions are allowed before study treatment must be permanently discontinued.

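### Table 14 shifts Cycle 2 Day 4 PK sampling only at Level 5, so at dosing Levels 3 and 4 the postdose samples would have no same-day dose

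*Combined protocol and SAP*

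**What the plan says.** Section 8.4, Table 14, labels Cycle 2 Day 4 a dosing day. It asks for a predose sample and samples at 1, 2 and 4 hours postdose, each paired with an ECG. The row carries one day-shift footnote, e: "If the oral decitabine/cedazuridine dosing level falls below Level 4", as set out in Table 9, "the timing of PK acquisition at this time point will be adjusted to be 1 day earlier".

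The Cycle 1 Day 4 row carries footnote e and also footnote a: "If there are 2 or more dose reductions, then PK should be done on Day 3 and Day 4" in place of Days 4 and 5. Footnote a is not attached to the Cycle 2 row, and the Day 4 and Day 5 pair that it names is sampled only in Cycle 1.

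Table 9 (Section 6.6.1) starts at Level 1, "Oral decitabine/cedazuridine Daily×5 for each 28-day cycle". Levels 2 and 3 are four and three daily doses. Level 4 is "Oral decitabine/cedazuridine on Days 1, 3, and 5 of each 28-day cycle". Level 5 is "Discontinue oral decitabine/cedazuridine".

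Section 4.1.1 describes dosing as falling to Level 5, so a fall means a higher level number. Section 9.5 applies any adjustment made in the DLT cohort to the rest of the study. Footnote n of Table 1 also places Cycle 2 predose and postdose sampling on Day 4. It has no level-dependent shift of its own and refers to Table 14 for details.

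**The concern.** A one-day shift is useful only where Day 4 is not a dosing day and Day 3 is. Footnote e takes effect at a level with no drug to measure and does nothing at the two levels where the shift is needed. Followed as written at Level 3 or 4, the Cycle 2 samples labelled 1, 2 and 4 hours postdose, and their ECGs, would refer to no dose given that day.

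What is at stake is the Cycle 2 PK data, four samples per subject, at the schedule carried forward. PK is a secondary objective (Section 3.0). No primary endpoint is involved.

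**Working it through.** **Step 1. Dosing days against the sampling day.** Inputs are Table 9 for the levels and Table 14 for the sampling days and footnotes. Table 9 does not list the days for Levels 2 and 3; I take them as Days 1 to 4 and Days 1 to 3.

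| Level | Dosing days | Cycle 2 sampling day (footnote e) | Dose that day? | Cycle 1 serial profile day (footnote a) | Dose that day? |
|---|---|---|---|---|---|
| 1 | 1 to 5 | 4 | Yes | 4 | Yes |
| 2 | 1 to 4 (assumed) | 4 | Yes | 4 | Yes |
| 3 | 1 to 3 (assumed) | 4 | No | 3 | Yes |
| 4 | 1, 3, 5 | 4 | No | 3 | Yes |
| 5 | none | 3 | No | 3 | No |

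Two reductions from Level 1 is Level 3, so footnote a works from Level 3 onward. On the Cycle 1 Day 4 row, footnote a moves sampling at Levels 3 and 4 while footnote e does not.

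**Step 2. A numeric reading.** If below Level 4 meant Levels 1 to 3, Level 3 would move to Day 3, a dosing day. Level 4 would still be sampled on Day 4 without a dose, and the unreduced Level 1 schedule would shift too, against the table's own default. This reading does not repair the footnote.

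**Step 3. How likely the cohort is to settle at Level 3 or 4.** The plan gives no figure. Use the Section 4.1.1 algorithm with the same DLT rate p at every level, all DLTs attributed to the oral drug, and q = 1 − p.

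- Fail Level 1 (2 or more of 6): F1 = 1 − q^6 − 6·p·q^5
- Pass a later level (0 of 3, or 1 of 3 then 0 of 3): S = q^3 + 3·p·q^2·q^3
- Fail a later level: F = 1 − S
- Settle at Level 3: F1·F·S. Settle at Level 4: F1·F·F·S

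For p = 0.20: F1 = 1 − 0.2621 − 0.3932 = 0.345 after rounding; S = 0.512 + 0.197 = 0.709; F = 0.291.

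| p | F1 | F | S | Reach Level 3 (F1·F) | Settle at 3 | Settle at 4 | Settle at 3 or 4 |
|---|---|---|---|---|---|---|---|
| 0.20 | 0.345 | 0.291 | 0.709 | 0.100 | 0.071 | 0.021 | 0.092 |
| 0.30 | 0.580 | 0.506 | 0.494 | 0.293 | 0.145 | 0.073 | 0.218 |
| 0.40 | 0.767 | 0.691 | 0.309 | 0.530 | 0.164 | 0.113 | 0.277 |

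Failing Levels 1, 2 and 3 uses 6 + 6 + 6 = 18 subjects, the approximate maximum in Section 4.1.1. If that were a hard limit, only the Level 3 column would count: about 7%, 14% and 16%.

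**Step 4. With the stopping rule.** Section 4.1.1 also invokes the excess-toxicity rule of Section 9.5. I simulated the same algorithm with the Table 17 boundary checked after every subject and DLTs pooled over levels. The chance of reaching Level 3 falls to about 6%, 13% and 15%, and the chance of settling at Level 3 or 4 to about 5%, 7% and 5%.

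**The case against.** A reader might infer that the PK schedule as a whole fails under dose reduction. The documents do not support that. Footnote a moves the Cycle 1 serial profile (predose plus eight postdose times) and the next-day sample from Level 3 onward, so the richest PK data at a reduced level are kept. Only the sparse Cycle 2 check is exposed.

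A reader might also take the chance of reaching Level 3, up to 53% at a 40% DLT rate, as the size of the problem. That includes paths that go on to Level 5 and leaves out the stopping rule. It also holds the DLT rate constant across levels, although the reductions are meant to lower it.

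Other points for the plan stand in part:

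- The row is labelled a dosing day and its samples postdose, so a site with no Day 4 dose would probably query the conflict. Table 14 and footnote n also allow ad hoc samples. Both soften the effect, but they rely on sites noticing.
- For individual subjects, the note to Table 9 allows at most two reductions outside DLT assessment. A subject starting at Level 1 could therefore get no further than Level 3, and is unlikely to be there by Cycle 2 Day 4.
- It would go too far to say that footnote e could never apply. Section 4.1.1 allows the protocol to be amended at Level 5 to modify dosing, so a later schedule below Level 4 is conceivable. Table 9 contains none now.

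The author may have meant fewer than four daily doses. The footnote says Level 4 and points to Table 9, and that intention would call for the same correction.

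**Conclusion.** The inconsistency holds for the Cycle 2 Day 4 row. Footnote e triggers only where the drug is stopped, and no other text moves that row at Levels 3 and 4. On the Cycle 1 Day 4 row the harm is avoided by footnote a, but two different triggers remain.

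The size is small and conditional: four Cycle 2 samples with paired ECGs per subject at Level 3 or 4. Because a cohort adjustment is carried forward, most later subjects would be affected if the cohort settled there. On the assumptions above, that chance is about 9%, 22% and 28% at DLT rates of 20%, 30% and 40% without the stopping rule, and about 5%, 7% and 5% with it. These figures cover cohort-level settling only; an individual reduction after the cohort settled at Level 2 would add some subjects.

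The Level 3 result assumes that three daily doses means Days 1 to 3. The Level 4 result needs no such assumption, since its days are listed. This is an internal inconsistency that would be good to correct; it does not threaten the trial's main conclusions.

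**What to change.** Reword the trigger in footnote e to the Table 9 levels at which Day 4 is not a dosing day, Levels 3 and 4. This agrees with footnote a's trigger of two or more reductions. Cycle 2 sampling then moves to Day 3, a dosing day at both levels and the same day as the shifted Cycle 1 profile. Levels 1 and 2 stay on Day 4.

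Align footnote a with the same trigger, preferably as one shared footnote, so that the shift cannot be applied twice to the Cycle 1 rows. Add the same shift to footnote n of Table 1. The sponsor should also confirm which days the three-dose schedule denotes.

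The cost is an edit to three footnotes. No samples or ECGs are added, and no dosing rule changes.

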## **8.5 Adverse Events, Serious Adverse Events, and Other Safety Reporting**

The definitions of AEs or SAEs can be found in Section [10.5](#).

### **8.5.1 Time Period and Frequency for Collecting Adverse Events and Serious Adverse Event Information**

All AEs and SAEs will be collected from the time the ICF is signed until 30 days after the last dose of study treatment. Any clinically significant findings that begin before the start of study treatment but after the ICF is signed will be recorded on the Medical History/Current Medical Conditions section of the eCRF, not in the AE section. However, if the event is related to a screening procedure it will be captured and recorded as an AE in the eCRF. Any clinically significant finding(s) observed after the start of study treatment will be recorded as an AE in the eCRF.

If the subject starts a new anti-cancer treatment, including a new investigational treatment, the stop date for reporting obligations for this study will be based on whichever occurs earlier (ie, 30 days after the last dose of study drug or initiation of a new anticancer therapy). Details for recording AEs and SAEs are provided in Section [10.5](#).

All SAEs will be recorded and reported to the sponsor or designee within 24 hours after the investigator is aware of the SAE, as indicated in Section [10.5](#). The investigator will submit any updated SAE data to the sponsor within 24 hours of the data becoming available.

Investigators are not obligated to actively seek AE or SAE information  $\geq 30$  days after the last dose of study treatment. However, if the investigator becomes aware of an SAE or of a death at any time beyond 30 days after the last dose, and he/she considers the event to be reasonably related to the study treatment or study participation, the investigator must promptly notify the sponsor as described in Section [10.5.4](#).

### **8.5.2 Method of Detecting Adverse Events and Serious Adverse Events**

The method of recording, evaluating, and assessing causality of AE and SAE and the procedures for completing and transmitting SAE reports are provided in Section [10.5](#).

Care should be taken not to introduce bias when detecting AEs and/or SAEs. Open-ended and non-leading verbal questioning of the study subject is the preferred method to inquire about AE occurrences (such as “Have you had any new symptoms, injuries, illnesses since your last visit?”).

### **8.5.3 Follow-up of Adverse Events and Serious Adverse Events**

After the initial AE/SAE report, the investigator is required to proactively follow each subject at subsequent visits/contacts. All SAEs will be followed until clinically relevant information is complete and reported to the sponsor; details are provided in Section [10.5.3](#).

Additional information for follow-up requirement of AEs/SAEs is provided in Section [10.5.3](#).

#### **8.5.4 Regulatory Reporting Requirements for Serious Adverse Events**

- The sponsor will comply with country-specific regulatory requirements relating to safety reporting to the regulatory authority, IRB/IEC, and investigators.
- Investigator safety reports must be prepared by the sponsor or sponsor's designee for suspected unexpected serious adverse reactions according to local regulatory requirements and sponsor policy and forwarded to investigators as necessary.
- An investigator who receives an investigator safety report describing a SAE or other specific safety information (eg, summary or listing of SAEs) from the sponsor will review and then file it along with the IB and will notify the IRB/IEC, if appropriate according to local requirements.

#### **8.5.5 Pregnancy**

- Details of all pregnancies in female subjects will be collected after the start of study treatment and until 180 days plus 5 half-lives of magrolimab (70 days), totaling 250 days (approximately 8.5 months), after the last dose of either study treatment. Details of pregnancies in female partners of male subjects will be collected after the start of study treatment and until 90 days plus 5 half-lives of magrolimab (70 days), totaling 160 days (approximately 5 months), after the last dose of either study treatment.
  - Magrolimab has a longer half-life than oral decitabine/cedazuridine, which forms the basis of the requirements above.
- If a pregnancy is reported, the investigator should follow the procedures outlined in Section 10.2.

The investigator should counsel any female subject with a positive pregnancy test after the start of treatment, discussing any risks of continuing the pregnancy and any possible effects on the fetus. The investigator will record any occurrence of pregnancy on the Pregnancy Exposure Report Form Part I and email to Astex Clinical Safety and Risk Management (CS&RM; [[contact]](mailto:[contact])). After the outcome of the pregnancy, collect information by completing the Pregnancy Exposure Report Form Part II.

#### **8.5.6 Definition of Dose-limiting Toxicities**

Dose-limiting toxicities are defined as any of the following toxicities at least possibly related to the treatment regimen as determined by the DSRC:

- Drug-related Grade  $\geq 3$  non-hematologic events (except nausea, vomiting, or diarrhea if the events do not require tube feeding, total parenteral nutrition, or require or prolong hospitalization).
- Grade 4 neutropenia and thrombocytopenia, not present prior to dosing, that last 28 days or longer should be considered a DLT unless clearly and solely due to the underlying disease.

- If the investigator suspects that the development of Grade 4 neutropenia or thrombocytopenia is drug related and the event continues for 7 days in Cycle 1, a BM assessment (no later than the 14th day of Grade 4 cytopenia) may be done, at the discretion of the investigator, to assist with the determination of DLT.
- Delay of >2 weeks after Cycle 1 is complete due to drug-related toxicity. That is, if initiation of Cycle 2 is delayed for drug-related toxicity, the DLT window will expand accordingly.
- Establishment of an MTD is not a goal of this study. However, the DSRC will assess the occurrence of DLTs in the DLT cohort (Section 4.1.1) to help ensure the study drug combination is safe. The DLT period has been defined as the first 2 cycles of oral decitabine/cedazuridine (from the start of administration to Cycle 1 Day 28) in the first 6 to approximately 18 subjects.

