- q Reporting of concomitant medications starts from 14 days before treatment and ends 30 days after the last dose of study treatment. Reporting of AEs starts at the signing of the informed consent form and ends 30 days after the last dose of study treatment.
- r Recording transfusions: Record all blood and platelet transfusions from 56 days before the start of study treatment through 30 days after the last dose of study treatment and in long-term follow up for subjects who discontinue treatment before documented disease progression until disease progression is documented.
- s BM aspirate/biopsy: Screening BM will be accepted up to 6 weeks prior to first dose; however, cytogenetics is required. If a subject undergoes SCT, they will continue to be followed using BM aspirate/biopsy per SOC for SCT. Cytogenetic data will be collected from the BM aspirate/biopsy sample each time a BM aspirate/biopsy is performed. Postdosing BM is to be performed on Day 1 (or within a 3-day window prior to Day 1) of Cycles 3, 5, and 7, and every 3 cycles thereafter (or within a 7-day window), as well as at the end of treatment or at disease progression, whichever is earlier. If the investigator suspects that the development of Grade 4 neutropenia or thrombocytopenia is drug related and the event continues for 7 days in Cycle 1 or 2, a BM assessment (no later than the 10th day of Grade 4 cytopenia) may be done, at the discretion of the investigator, to assist with determination of DLT. If hematologic recovery is in progress, a repeat CBC may be done no more than 7 days after the BM evaluation for response assessment. BM evaluation may occur as clinically indicated to monitor DOR as appropriately guided by PB counts after achieving a confirmed CR but should occur at least every 3 cycles for the first year, then as clinically indicated at additional time points. MRD will be obtained per local standard of care.

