### 4.0 STUDY DESIGN

#### 4.1 Overall Design

This is a Phase 2, open-label, multicenter, non-randomized interventional study to evaluate the safety, efficacy, and PK of oral decitabine/cedazuridine when given in combination with magrolimab for the treatment of subjects with previously untreated intermediate- to very high-risk MDS. Subjects with higher-risk MDS (IPSS-R  $\geq 3.5$ ) will be screened for participation with the goal of obtaining approximately 100 subjects who are evaluable, those subjects receiving one or more dose of study treatment, for the primary study endpoint. The first 6 to approximately 18 subjects enrolled will be evaluated for dose-limiting toxicities (DLTs) during the first 2 cycles of oral decitabine/cedazuridine and will be used to confirm the dosing for oral decitabine/cedazuridine in combination with magrolimab. In this protocol, a cycle is defined as a

cycle of oral decitabine/cedazuridine, which is normally 28 days. Dose-limiting toxicities are defined in Section 8.5.6.

The primary analysis of the CR rate will be conducted approximately 8 months after enrollment of approximately 100 subjects has occurred. Participation will include screening, treatment, and follow-up. The screening period will last up to 21 days before the first dose of study treatment, during which time the participant's eligibility and baseline characteristics will be determined. Subjects will receive study treatment per the dosing schedule in [Table 3](#) and [Table 4](#). Study treatment may be continued until disease progression (including treatment failure by the International Working Group [IWG] 2006 criteria or relapse after PR/CR), or unacceptable toxicities occur, the subject is withdrawn from study treatment, or the sponsor stops the study. In case subjects choose to discontinue the study treatment due to reasons other than disease progression, eg, voluntary withdrawal, subjects will be followed up for response assessments until documented disease progression occurs. For subjects who stop receiving the study treatment to receive a stem cell transplant (SCT), follow-up for response assessment and collection of SOC BM biopsy/aspirate results will continue until documented disease progression occurs or start of new anticancer therapy, whichever occurs first. Then subjects will be observed for survival until death, withdrawal of consent, or the end of the study, whichever occurs first.

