#### 4.1.1 Dose-Limiting Toxicity Cohort

[figure not shown]
The first 6 to approximately 18 subjects enrolled, the DLT cohort, will be evaluated to confirm that the dosing of oral decitabine/cedazuridine in combination with magrolimab is well tolerated (Section 8.5.6). Due to the low incidence of magrolimab DLTs (please reference Investigational New Drug [IND] 147229 for the magrolimab Investigator Brochure), it is expected that most DLTs will be related to oral decitabine/cedazuridine, especially those related to neutropenia, thrombocytopenia, GI toxicity, and infection. Thus, a DLT should generally be considered related to oral decitabine/cedazuridine unless the investigator feels that a DLT is related to magrolimab. The DLT period will last the first 2 cycles of oral decitabine/cedazuridine treatment as defined in Section 4.1. Evaluation of the cohort will end when a tolerated dosing is identified, or the study is stopped due to toxicity. Oral decitabine/cedazuridine and magrolimab dosing will initiate as outlined in Section 4.5. If there are DLTs associated with magrolimab that occur in the DLT cohort, the investigator in consultation with the Astex medical monitor and the Data and Safety

Review Committee (DSRC) will determine if a dose modification of magrolimab is appropriate (see Section [6.6.2](#) for magrolimab dose modification recommendations).

The dosing reduction process for oral decitabine/cedazuridine-associated DLTs will follow a 3+3 design ([Figure 2](#)), as follows:

- The first 6 subjects will be evaluated for myelosuppression and other DLTs (Section [8.5.6](#)).
- If fewer than 2 subjects among the first 6 (<33%) experience a DLT (Section [8.5.6](#)), the current dosing level will be maintained, and no further DLT cohort evaluation will be conducted.
- If a DLT occurs in 2 or more of the initial 6 subjects, then oral decitabine/cedazuridine dosing will be reduced 1 level ([Table 9](#)) and 3 more subjects will be enrolled at that dosing level.

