#### **4.3 Data and Safety Review Committee**

The DSRC will comprise the principal investigators (or designees), and the Astex medical monitor, clinical pharmacologist, and lead statistician, and other study team members as appropriate.

The DSRC will review emerging safety data after the first 6 subjects are enrolled. The first 6 to approximately 18 subjects enrolled will be evaluated for DLTs during the first 2 cycles; if present (following standard 3+3 design), there will be dosing reductions of oral decitabine/cedazuridine which will be applied to all subsequent subjects.

Further details of the DLT cohort are provided in Section [4.1.1](#).

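### Section 8.5.6 ends the 2-cycle DLT period at Cycle 1 Day 28 (it should be Cycle 2 Day 28) and has no rule for a Grade 4 cytopenia still open when the period closes

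*Combined protocol and SAP*

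**What the plan says.** Section 8.5.6 holds the working definition of a DLT, and Sections 4.1 and 4.1.1 refer to it. On the observation period it says: "The DLT period has been defined as the first 2 cycles of oral decitabine/cedazuridine (from the start of administration to Cycle 1 Day 28".

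Elsewhere the period is two cycles with no such end day. Section 4.1 says the first subjects "will be evaluated for dose-limiting toxicities (DLTs) during the first 2 cycles of oral decitabine/cedazuridine". Section 4.1.1 says "The DLT period will last the first 2 cycles of oral decitabine/cedazuridine treatment". The synopsis and Section 4.3 agree.

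The hematologic criterion in Section 8.5.6 is "Grade 4 neutropenia and thrombocytopenia, not present prior to dosing, that last 28 days or longer should be considered a DLT", unless the event is clearly and solely due to the disease. The only stated extension of the window is for a delayed start of Cycle 2.

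Two places describe an optional marrow to help decide whether a cytopenia is a DLT. Section 8.5.6 applies it where "the event continues for 7 days in Cycle 1, a BM assessment (no later than the 14th day of Grade 4 cytopenia"). Table 1, footnote s, applies it where "the event continues for 7 days in Cycle 1 or 2, a BM assessment (no later than the 10th day of Grade 4 cytopenia").

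The decision that depends on these definitions is in Section 4.1.1: "If fewer than 2 subjects among the first 6 (<33%) experience a DLT", the dose is kept and the DLT cohort evaluation ends. On committee timing, Section 4.3 says: "The DSRC will review emerging safety data after the first 6 subjects are enrolled".

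**The concern.** The stated end day halves the period that the same sentence describes. It is the only calendar end point given for the DLT window, and it stands in the definition that sites and the DSRC will consult.

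Correcting it leaves a second question. A criterion that takes 28 days to meet sits inside a 56-day window, so most cytopenias that begin in Cycle 2 will be neither met nor ruled out when the window closes, unless they have already recovered. The plan does not say whether such an event counts by its onset, or whether the subject stays unclassified until it resolves.

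This matters because the cohort decision is final in one direction. With 0 or 1 DLT among the first 6, the starting dose is carried forward and the cohort evaluation stops. Section 4.1.1 itself names neutropenia and thrombocytopenia among the DLTs it expects. A prolonged cytopenia left out at that point could turn a reduction into a dose kept.

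**Working it through.** **Inputs.** Cycle length normally 28 days (Section 4.1); hematologic DLT at 28 days or more (Section 8.5.6); dose kept if fewer than 2 of 6 have a DLT (Section 4.1.1); blood-count schedule from Tables 1 and 2; boundary from Table 17.

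**1. End of the window.** 2 × 28 = 56, so two cycles end on Cycle 2 Day 28 (Day 56). The stated Cycle 1 Day 28 is Day 28. The figure does not reproduce.

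**2. Latest onset that can complete 28 days inside the window.** End day − 28 + 1.
- Day 28 as written: 28 − 27 = Day 1.
- Day 56 as corrected: 56 − 27 = Day 29.

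**3. Open events after the correction.** Onset on Cycle 2 Day d is Day 28 + d. Its 28th day is 28 + d + 27 = Day 55 + d, which is Day 56 or earlier only for d = 1. An event still present at Day 56 therefore needs d − 1 more days: 7 for d = 8, 14 for d = 15, 27 for d = 28.

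**4. Can the duration be observed?** After Day 57 scheduled counts are 14 days apart (Days 57, 71, 85).
- Onset seen on Day 36: 28th day is Day 63, between Day 57 (22nd day of the event) and Day 71 (36th day).
- Onset seen on Day 43: 28th day is Day 70, between Day 57 (15th) and Day 71 (29th).
- Onset seen on Day 50: 28th day is Day 77, between Day 71 (22nd) and Day 85 (36th).

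Recovery between two such draws leaves the duration undetermined. Weekly counts add one draw (about Day 64) for the first two cases and two draws (about Days 64 and 78) for the third.

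**5. Illustration of the stakes. Every rate here is an assumption.** Suppose 20% of subjects have a DLT that is counted in any case, and a further 2%, 5% or 10% have only a prolonged Cycle 2 cytopenia. P(dose kept) = P(X ≤ 1), X ~ Binomial(6, p) = (1 − p)^6 + 6p(1 − p)^5.

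| Added rate | None of the added events counted (p = 20%) | All counted | Difference | Difference if half are missed |
|---|---|---|---|---|
| 2% | 0.655 | 0.606 (p = 22%) | 0.05 | 0.02 |
| 5% | 0.655 | 0.534 (p = 25%) | 0.12 | 0.06 |
| 10% | 0.655 | 0.420 (p = 30%) | 0.24 | 0.11 |

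**6. Effect of the Section 9.5 boundary.** An exact recursion over Table 17 gives a crossing probability of 0.199 at a 20% DLT rate, which reproduces the plan's limit of 20%. Now take the probability that the dose is kept and the boundary is not crossed, with every event counted by Table 17 and no reporting lag. Each pair below compares none of the added events counted at the first-6 decision with all of them counted.
- By n = 40: 0.594 against 0.560, 0.521 against 0.453, 0.350 against 0.274. Differences 0.03, 0.07, 0.08.
- By n = 100: 0.527 against 0.498, 0.375 against 0.330, 0.126 against 0.102. Differences 0.03, 0.045, 0.02.

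The boundary reduces the effect but is not the same test. At n = 6 it requires 4 subjects with DLTs, where the dose rule requires 2.

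**7. The two marrow rules.** They differ on cycle (1 only; 1 or 2) and on deadline (14th day; 10th day). A marrow on the 12th day meets one and breaks the other.

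**The case against.** The end day is plainly a slip. The same sentence says 2 cycles, four other places agree, and Section 8.5.6 extends the window when Cycle 2 starts late, which would be pointless if the window closed at the end of Cycle 1. This stands. A reader might infer that DLTs will be observed for one cycle only, and the documents do not support that.

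On open events, a reader might infer that the dose decision is taken at Day 56, or once 6 subjects are enrolled, and that late cytopenias will be scored as non-DLTs. The documents do not say so. No section sets a Day 56 decision. Section 4.3 speaks of reviewing emerging data, and its next sentence has subjects evaluated over 2 cycles. Section 8.5.6 leaves DLT status to the DSRC, which could count by onset or wait. Footnote s, by covering Cycle 2, suggests that Cycle 2 cytopenias are meant to count. This too stands, and it limits the point to an unstated convention.

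There are also safeguards: cycle delay at a neutrophil count of 500 cells/µL or below (6.6.1), withholding and a lower dose for the affected subject (6.6.3), DSRC review after about 20 subjects with at least 2 cycles, ad hoc meetings (1.1), the Section 9.5 boundary, and the sponsor's freedom to stop for safety. They protect subjects and could prompt action. None states how an open cytopenia is classified or provides that the 2-of-6 decision is revisited. The criterion for a delay of more than 2 weeks does not clearly help either, since it is explained only by the start of Cycle 2.

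The marrow is discretionary in both places, and a site that works to the 10th day also meets the 14th. That part is minor.

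**Conclusion.** The end day in Section 8.5.6 is wrong as written: Day 28 where two cycles give Day 56. This rests on the text and on 2 × 28, with no assumption beyond the normal cycle length.

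The open-event gap is real but smaller. After the correction, 27 of the 28 possible Cycle 2 onset days (Day 30 to Day 56) cannot complete the criterion inside the window, and no sentence covers them. Mis-scoring is possible, not certain.

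The probabilities in the working are illustrations. The documents give no rate for prolonged Cycle 2 cytopenia, and the largest difference, 0.24, needs a 10% rate with every such event missed. They show why the convention should be written down; they are not evidence of harm. The differing marrow rules are an inconsistency to tidy.

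The sponsor should make these changes: the definition feeds a final dose decision, and repair is cheap.

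**What to change.** 1. In Section 8.5.6, replace Cycle 1 Day 28 with Cycle 2 Day 28.
2. Add one sentence, for example: *A Grade 4 neutropenia or thrombocytopenia with onset in the first 2 cycles counts by onset; it is followed with weekly CBCs to recovery or 28 days before that subject is classified for the cohort dose rule.* Table 1, footnote o, already suggests considering weekly counts for Grade 3 or worse; for open events they should be required.
3. Use one marrow rule in Section 8.5.6 and footnote s: Cycle 1 or 2, with a single deadline. It can stay discretionary.

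**Cost.** Three wording changes; one or two extra CBCs per open event in the cases worked above; and a wait of d − 1 days past Day 56, at most 27, at any decision that has an open event. Counting one wait per level would give 3 × 27 = 81 days, but that understates the extreme. Under Section 4.1.1 a reduced level has a decision after 3 subjects and another after 6, so three levels of 6 (18 subjects) have 1 + 2 + 2 = 5 decisions and a worst case of 5 × 27 = 135 days. That needs the latest possible onset every time; an onset on Day 36 or Day 43 costs 7 or 14 days. Table 9 has a fourth active level, which this bound leaves out. The amendment should also say whether enrollment pauses during a wait.
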